### **3.2 Rationale for Trial Design**

In the trial, the dose escalation was planned with consideration of the subjects' safety and based on the "Guidelines for Clinical Evaluation of Antimalignant Tumor Drugs (Notification No. 1101001 of the Evaluation and Licensing Division, Pharmaceutical and Food Safety Bureau dated 01 Nov 2005)."

As mentioned in [Section 1.2.3](#) Trial Rationale, the doses and regimen were chosen based on evaluations of the safety, efficacy, and PD of SGI-110 in a clinical trial conducted outside of Japan (Study SGI-110-01), and it has been decided to adopt a study design to evaluate the tolerability in each cohort and gradually escalate the dose.

Since results of Study SGI-110-01 suggest that the recommended dose for non-Japanese patients is assumed to be 60 mg/m^2, the primary dose to be investigated has been set as 60 mg/m^2. This study is the first clinical trial of SGI-110 involving Japanese patients with AML and, therefore, in considering the subjects' safety, the initial dose will be 36 mg/m^2, which was one of the doses used in Study SGI-110-01 and is a lower dose than the primary dose of 60 mg/m^2. The maximum dose will be 90 mg/m^2, which was determined to be the MTD in Study SGI-110-01 and is suggested to be effective according to exploratory evaluation. In addition, the tolerability of SGI-110 at 60 mg/m^2 once daily for 10 days will be evaluated in Japanese patients in this study because the same dose and regimen is planned to be adopted in Study SGI-110-06 in patients with relapsed or refractory AML.

As mentioned in [Section 1.2.2](#) Clinical Study Results, occurrences of myelosuppression and decreased blood cell counts, and infections attributable to these, as well as

occurrences of digestive symptoms are anticipated following administration of SGI-110. Therefore subjects will be hospitalized during Course 1, when the IMP will be administered for the first time to them, so they can be carefully monitored. Thereafter, the subjects are to visit the trial site at least once weekly to undergo hematological tests for evaluation of decreased blood cell counts and to undergo a medical examination by a physician to check their general condition. In addition, a chest X-ray examination and blood biochemistry test are to be performed before the start of the next course in order to ensure the subjects' safety.

The subjects for the clinical trial are expected to have symptoms that may affect ADL such as decreased blood cell counts and infection associated with the progression of disease already present at study entry. Hence, supportive care used in routine medical practice is to be permitted, and arrangements will be made to prevent the subjects' quality of life from being undermined by participation in the trial.

The subjects for the trial will be patients who have relapsed after existing therapy or do not respond to treatment, and elderly patients aged 65 years or older who are not eligible for standard intensive chemotherapy; therefore they have limited treatment options. For ethical reasons, a subject will be allowed to continue with the IMP after the completion of the DLT evaluation period if they wish to do so as long as they have not experienced an AE during Course 1 (ie, the DLT evaluation period of the trial) that makes continuing the IMP difficult and have no evidence of disease progression. Safety and efficacy will be continuously evaluated during the primary evaluation part. For long-term safety evaluation after the end of the primary evaluation part, an extended treatment part will be included so that treatment can be continued for subjects who are on the IMP at that time if they consent to continue the treatment.

### **3.3 Endpoints**

#### **3.3.1 Safety**

##### **3.3.1.1 Primary Endpoint (Primary Evaluation Part)**

DLT

##### **3.3.1.2 Secondary Endpoints**

(Primary evaluation part)

AEs, clinical laboratory values, vital signs (blood pressure, pulse rate, body temperature), body weight, Eastern Cooperative Oncology Group (ECOG) PS, 12-lead electrocardiogram (ECG), chest X-ray

Protocol No. 343-14-001

(Extended treatment part)

AEs, clinical laboratory values

### **3.3.2 Efficacy Endpoints (Primary Evaluation Part)**

Complete remission rate (CR), composite complete remission rate (CR + CRi + CRp), overall remission rate (CR + CRi + CRp + partial response [PR]), overall survival, and composite complete remission duration

### **3.3.3 Pharmacokinetic Endpoints (Primary Evaluation Part)**

SGI-110 and decitabine plasma concentrations, PK parameters

### **3.3.4 Pharmacodynamic Endpoint (Primary Evaluation Part)**

Extent of DNA hypomethylation in LINE-1

#### **[Rationale for variable selection]**

[Safety]

Safety in each cohort is to be evaluated in accordance with the “Guidelines for Clinical Evaluation of Antimalignant Tumor Drugs” (Notification No. 1101001 of the Evaluation and Licensing Division, Pharmaceutical and Food Safety Bureau dated 01 Nov 2005). DLTs and AEs are to be assessed using the criteria used for toxicity assessment of other anticancer drugs (CTCAE version 4.0 of the US National Cancer Institute).

[Efficacy]

Efficacy is to be evaluated in accordance with the criteria used in a phase 1/2 trial conducted outside of Japan (Study SGI-110-01) which was a partially modified version of the response criteria for AML treatment established by an international working group.

[Pharmacokinetics]

SGI-110 and decitabine plasma concentrations in Japanese subjects are to be measured to evaluate PK parameters.

[Pharmacodynamics]

The extent of DNA hypomethylation, which is regarded as the main action of SGI-110, is to be measured.

### 3.4 Target Number of Patients

Maximum: 24 subjects

Cohort 1 (36 mg/m^2, 5 days): 3 to 6 subjects

Cohort 2 (60 mg/m^2, 5 days): 3 to 6 subjects

Cohort 3 (60 mg/m^2, 10 days [ie, 5-day administration twice, with a non-dosing period in-between]): 6 subjects

Cohort 4 (90 mg/m^2, 5 days): 3 to 6 subjects

### 3.5 Rules to Be Observed for Enrollment and Treatment

- 1) The dose or regimen should remain unchanged for each subject, and no subject should be re-enrolled.
- 2) In order to avoid occurrence of unexpected serious adverse drug reactions in multiple subjects, the IMP should be administered to the second subject after the following day of Day 1 of Course 1 in the first subject at each dose level.
- 3) When the administration or examination scheduled for Course 1 cannot be implemented for reasons other than safety, the subject should be excluded from the DLT evaluation, and another subject should be enrolled.
- 4) Administration of SGI-110 is expected to cause myelosuppression and infection (eg, febrile neutropenia, pneumonia, and sepsis). Delay or discontinuation of administration should be determined for subjects who have experienced or are suspected to have experienced pyrexia or infection based on data from laboratory tests, physical examination (body temperature), and imaging tests before the start of the next course and continuing the treatment.
- 5) In and after Course 2 (extended treatment period), IMP administration may be suspended (skipped) from Day 2 and onwards at the discretion of the investigator or subinvestigator, depending on the subject's condition. Subjects who fall under any of the discontinuation criteria should be withdrawn from the trial.

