**Definitions of Terms**

Term	Definition
Screen failure	A screen failure is a subject from whom written informed consent is obtained, but to whom the investigational medicinal product (IMP) is not administered.
Individual subject trial start date	The day of obtaining the subject's written informed consent.
Withdrawn subject	A subject who withdraws from the trial during Course 1 without completing dose-limiting toxicity (DLT) evaluation or who withdraws from the trial after completing DLT evaluation. (Subjects who withdraw during Course 1, which is the DLT evaluation period, and those who withdraw after the DLT evaluation will be distinguished.)
Individual subject trial discontinuation date	The day of the withdrawal examination to be performed within 5 days from the day when the investigator or subinvestigator determines that the subject is to be withdrawn from the trial.
Completer	A subject who receives the specified IMP during Course 1, completes examinations, and is evaluable for DLTs.
Individual subject trial completion date	The day when the examination scheduled for Day 29 of Course 1 is performed or the start day of Course 2, whichever is later.
Individual subject trial period	A period from the day of obtaining the subject's informed consent to the day of trial discontinuation. Does not include the follow-up or outcome investigation period.

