## 6 Trial Design

### 6.1 Dose, Regimen, and Treatment Period

The total daily dose will be determined based on the subject's body surface area (BSA) calculated from height and weight prior to administration in each course, according to the treatment cohort.

SGI-110 will be administered SC at the determined daily dose after being reconstituted using the custom diluent provided.

In Cohorts 1, 2, and 4, subjects will receive SGI-110 once daily for 5 consecutive days (Day 1 to Day 5), followed by a 23-day non-dosing period (Day 6 to Day 28). One course will consist of 4 weeks (28 days). In Cohort 3, subjects will receive SGI-110 once daily for 10 days in total (SGI-110 will be administered for 5 consecutive days [Day 1 to Day 5], suspended for 2 days [Day 6 and Day 7], then administered for another 5 consecutive days [Day 8 to Day 12]), and the dosing will be suspended for 16 days (Day 13 to Day 28). One course will consist of 4 weeks (28 days).

The dose and regimen for each cohort is as follows:

Cohort 1 ( $36 \text{ mg/m}^2$ , 5-day administration)

Cohort 2 ( $60 \text{ mg/m}^2$ , 5-day administration)

Cohort 3 ( $60 \text{ mg/m}^2$ , 10-day administration [ie, 5-day administration twice, with a non-dosing period in-between])

Cohort 4 ( $90 \text{ mg/m}^2$ , 5-day administration)

SGI-110 for injection, 100 mg contains SGI-110 equivalent to 100 mg of free acid, as a lyophilized powder in a 5-mL glass vial. Subjects who complete IMP administration and all observations during the DLT evaluation period, and who do not have any apparent progression of AML, will be permitted to continue treatment with IMP following the DLT evaluation period if they wish, and will receive treatment according to the same dosing schedule as Course 1 (Cohorts 1, 2, and 4).

In Cohort 3, subjects will receive SGI-110 for 10 days in Course 1 (DLT evaluation period), for 10 or 5 days in Course 2 (Extended treatment period), for 5 days in Course 3 and subsequent courses. The investigator will determine whether or not the transition to Course 2 should be postponed and which regimen is used for each subject, as described below, based on the subject's condition (the percentage of blasts in the peripheral blood and bone marrow, and peripheral blood cell counts) at the completion of Course 1.

- 1) Has blasts in the peripheral blood: Subject will proceed to Course 2 without delay and receive SGI-110 for 10 days.

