### 7.2.4 Pharmacokinetic Evaluation

Blood will be sampled and processed in accordance with the following procedures, and the plasma samples will be cryopreserved at  $\leq -70^{\circ}\text{C}$  (preset temperature) until collection

by the sample collecting facility. The sample collecting facility will transport the samples packed in dry ice to the laboratory performing drug concentration measurements.

1) Blood sampling

At each blood sampling timepoint, 6 mL of blood will be drawn into a tube containing tetrahydrouridine and di-potassium ethylenediaminetetraacetic acid (EDTA). The tube will be slowly inverted 8 to 10 times to mix the blood with these agents and kept in an ice bath until centrifugation. The sample tubes will be centrifuged within 2 hours after sampling at 1800 g and approximately 4°C for 10 minutes or at 1500 g and approximately 4°C for 15 minutes. The separated plasma will be transferred into two labelled polypropylene tubes (primary sample and backup sample). The date and time of blood sampling will be documented in the medical records and CRF.

2) Blood sampling timepoints

[Cohorts 1, 2, and 4]

Day 1 and Day 5: predose, 15 minutes, 30 minutes, 60 minutes, 90 minutes, 2 hours, 3 hours, 4 hours, 6 hours, 8 hours, and 24 hours (Day 5) after dosing

Day 2, Day 3, and Day 4: predose (predose on Day 2 is the same as 24 hours postdose on Day 1.)

[Acceptable time windows]

Day 1 and Day 5      Predose on Day 1: within 2 hours before IMP administration  
                            Predose on Day 5: ± 30 minutes of 24 hours from Day 4 dosing and before the Day 5 dosing  
                            15 minutes and 30 minutes postdose: ± 3 minutes  
                            60 minutes, 90 minutes, and 2 hours postdose: ± 6 minutes  
                            3 hours and 4 hours postdose: ± 12 minutes  
                            6 hours and 8 hours postdose: ± 24 minutes  
                            24 hours postdose: ± 30 minutes (24 hours postdose on Day 1 should be performed before Day 2 dosing)

Day 2, Day 3, and Day 4      Predose: ± 30 minutes of 24 hours from the previous dosing and before the dosing on that day

[Cohort 3]

Day 1 and Day 12: predose, 15 minutes, 30 minutes, 60 minutes, 90 minutes, 2 hours, 3 hours, 4 hours, 6 hours, 8 hours, and 24 hours after dosing

Day 5: 90 minutes and 6 hours after dosing

[Acceptable time windows]

Day 1 and Day 12      Predose on Day 1: within 2 hours before IMP administration  

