5.1.1.1 Dose-limiting Toxicity Analysis Set

The DLT analysis set will include subjects in whom tolerability has been assessed in Cohorts 1 to 4 (subjects who have received all doses and completed all assessments scheduled for the DLT evaluation period).

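### The replacement rule and the DLT analysis set turn on any missed Course 1 item, disagree about misses for safety reasons, and leave the maximum of 24 without a replacement allowance or a label

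*Protocol*

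**What the plan says.** Section 3.5, rule 3), of the protocol provides that if "administration or examination scheduled for Course 1 cannot be implemented for reasons other than safety, the subject should be excluded from the DLT evaluation". The rule then calls for a replacement: "and another subject should be enrolled". It does not say which examinations count.

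Protocol 11.1.1.1 and SAP 5.1.1.1 define the DLT analysis set in the same words: "subjects who have received all doses and completed all assessments scheduled for the DLT evaluation period". Protocol 11.3.1.1 and SAP 9.2 analyse the primary endpoint in that set. The Definitions of Terms describe a completer as "A subject who receives the specified IMP during Course 1, completes examinations, and is evaluable for DLTs".

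Protocol 3.4 gives "Maximum: 24 subjects": 3 to 6 in each of Cohorts 1, 2 and 4, and 6 in Cohort 3. Section 3.1 fills Cohorts 2 and 3 to six even if the first three subjects have no DLT. Nothing states whether these are treated or DLT-evaluable subjects.

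Table 7.1-1 marks Course 1 PK and PD sampling as mandatory. For the 5-day cohorts, section 7.2.4 lists "Day 1 and Day 5: predose, 15 minutes, 30 minutes, 60 minutes, 90 minutes, 2 hours" and continues to 24 hours.

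**The concern.** The condition for counting in the primary endpoint should be that DLT status could be judged. The plan instead uses completeness of the whole Course 1 schedule, much of which serves PK and PD.

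Three things are at stake. A subject whose DLT status is known can be lost to the primary endpoint, and a further patient with AML dosed, for a reason unrelated to tolerability. The two provisions treat a miss for safety reasons differently, and the analysis set as worded leaves out subjects who matter most to a tolerability endpoint. The stated sample size, which section 13.3.2 requires to be given to patients, makes no allowance for the replacements that the rule creates.

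**Working it through.** **1. The provisions side by side, applied literally**

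| Subject in Course 1 | Section 3.5, rule 3) | DLT analysis set |
|---|---|---|
| A. All doses, full toxicity follow-up, one PK or PD sample missed for a non-safety reason | Excluded and replaced | Out |
| B. Dosing stopped because of a DLT | Not excluded (safety reason) | Out |
| C. Has a DLT, then misses an examination for a non-safety reason | Excluded and replaced | Out |
| D. No DLT, a dose missed for a safety reason | Not excluded | Out |

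Rows B and D are the conflict between the provisions. Rows A and C are the over-wide trigger.

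**2. What one subject can do.** Section 3.1 blocks transition at two or more of six subjects with a DLT. In row B, with two DLTs among six, the primary table would show 1/5 = 20% instead of 2/6 = 33%. In row C, the count falls from 2/6 to 1/5. If the replacement has no DLT it becomes 1/6, which permits transition.

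**3. How many items can trigger the rule.** PK draws per subject (protocol 7.2.4), with the Day 2 predose and the Day 1 24-hour sample counted once:
- Cohorts 1, 2 and 4: 11 (Day 1) + 1 (Day 3) + 1 (Day 4) + 11 (Day 5) = 24.
- Cohort 3: 11 (Day 1) + 2 (Day 5) + 11 (Day 12) = 24.

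PD sampling adds five (Days 1, 8, 15, 22 and 29). The documents give no miss rate. If every missed PK draw counted and misses were independent at rate m, the share of subjects excluded would be 1 − (1 − m)^24: 2.4% at m = 0.1%, 11.3% at 0.5% and 21.4% at 1%.

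**4. The stated maximum.** 6 + 6 + 6 + 6 = 24 reproduces the figure, with nothing left for replacements. If all four cohorts are opened and completed, Cohorts 1 and 4 end at 3 or 6 and Cohorts 2 and 3 at 6. The evaluable total is therefore 18, 21 or 24, leaving room for 6, 3 or 0 replacements under 24.

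Let d be an assumed share of subjects lost for non-safety reasons, with replacements subject to the same loss. The chance that more than 24 are treated is:

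| Evaluable total | d = 2% | d = 5% | d = 10% |
|---|---|---|---|
| 18 | <0.1% | <0.1% | 0.8% |
| 21 | 0.1% | 3.0% | 21% |
| 24 | 38% | 71% | 92% |

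The bottom row is 1 − (1 − d)^24. It applies only when Cohorts 1 and 4 both expand. With one common DLT rate p, the chance of that path is [3p(1 − p)² × (1 − p)³] × [(1 − p)^6 + 6p(1 − p)^5] × [3p(1 − p)²]. These factors are Cohort 1 expanding and passing, Cohort 2 passing, and Cohort 4 expanding. The result is 1.5%, 3.8%, 4.9% and 2.8% at p = 5%, 10%, 20% and 30%.

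**5. Cohorts 2 and 3.** Once each must yield six evaluable subjects, there are 12 places and no slack within the cohort. P(at least one replacement) = 1 − (1 − d)^12 = 22%, 46% and 72% at d = 2%, 5% and 10%. Expected replacements are 12/(1 − d) − 12 = 0.2, 0.6 and 1.3.

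**The case against.** The best reply is that the literal reading is extreme. No passage says that a missed PK draw triggers replacement. On dosing days, section 7.1.4 introduces PK sampling in a sentence separate from its list of examinations. Course 1 is inpatient, so misses should be few, and they would probably cluster within subjects rather than fall independently. SAP section 4 also provides for confirming who is included before the final analysis.

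This weakens the PK illustration but does not remove the point. PD sampling stands inside the examination lists for Days 8, 15, 22 and 29, the analysis set requires all assessments without exception, and nothing exempts either type of sample.

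Four stronger readings are tempting and not supported:
- A reader might infer that 24 must be exceeded. It is certain to be only if all four cohorts reach six evaluable subjects, at least one is replaced, and 24 means treated subjects. Sections 3.1 and 11.5 speak of evaluation in six subjects, so 24 may well mean evaluable.
- A reader might infer that excluded subjects' data are lost. They stay in the safety set, where protocol 11.3.1.2 and SAP 9.3.1 also tabulate DLTs.
- A reader might infer that items such as chest X-ray have no bearing on a DLT. Under 7.2.1.6 and 7.2.1.7, clinically significant ECG and X-ray findings are assessed as AEs, and a related Grade 3 or higher non-haematologic toxicity can be a DLT.
- A reader might infer a contradiction over continuation into Course 2 between 6.1 and 3.2. Section 3.2 also presupposes that the DLT evaluation period has been completed, so the texts are compatible.

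**Conclusion.** The point holds as a defect of wording with consequences for the primary endpoint. The mismatch over safety reasons, the absence of any limit to DLT-relevant items, and the unlabelled maximum with no replacement allowance all follow from the text without any assumed rate.

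The size is less certain. Every miss, loss and DLT rate above is an assumption, and the 38%, 71% and 92% are conditional on a path with a probability of about 1.5% to 5%. The cohort-level figures of 22%, 46% and 72% need only that Cohorts 2 and 3 are filled to six evaluable subjects, and they apply to the stated cohort sizes, not to 24.

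It should not be inferred that transition decisions would ignore a subject whose dosing stopped for a DLT. Section 3.1 counts subjects with a DLT in the cohort and does not refer to the analysis set, so row B affects the primary table. Row C could affect a decision, because rule 3) removes that subject from the DLT evaluation itself.

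**What to change.** 1. Align section 3.5, rule 3), protocol 11.1.1.1 and SAP 5.1.1.1, with the completer definition following. The DLT set should contain:
   - every treated subject who has a DLT in the evaluation period; and
   - subjects without a DLT who received the scheduled Course 1 doses, or missed doses only for safety reasons, and who have the assessments needed to judge the DLT criteria: AE and medical examination, vital signs (fever is part of the febrile neutropenia definition), haematology, biochemistry, and imaging or ECG where needed to assess an AE.

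   State that a missed PK, PD or other sample not used to judge a DLT neither excludes nor replaces a subject.
2. In section 3.4 and the synopsis, label 24 and the cohort sizes as DLT-evaluable subjects, with replacements additional.

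The cost is wording, and a maximum that no longer caps the number treated. No procedure is added. Timing needs care: the SAP rests on protocol version 8 of 13 Oct 2017, after the 25 Aug 2017 data lock for Cohorts 1, 2 and 4. For those cohorts the change to the set would follow the lock. Its timing and reason belong in the study report under section 11.4, and showing DLT counts under both definitions would make any effect visible.

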## 4 Investigational Medicinal Products

### 4.1 Test Product and Comparator

#### 4.1.1 Test Product

Code Name	SGI-110
Generic Name	Undecided
Chemical Name	Sodium (2R,3S,5R)-5-(4-amino-2-oxo-1,3,5-triazin-1 (2H)-yl)-2-(hydroxymethyl) tetrahydrofuran-3-yl ((2R,3S,5R)-5-(2-amino-6-oxo-1H-purin-9 (6H)-yl)-3-hydroxytetrahydrofuran-2-yl) methyl phosphate
Content and Formulation	SGI-110 for injection, 100 mg contains SGI-110 equivalent to 100 mg of free acid, as a lyophilized powder in a 5-mL glass vial. SGI-110 diluent

Code Name	SGI-110
	for reconstitution, 3 mL contains 3 mL of custom diluent for reconstitution in a 5-mL glass vial.
Storage Conditions	SGI-110 for injection, 100 mg: 2°C to 8°C SGI-110 diluent for reconstitution, 3 mL: 2°C to 30°C

#### **4.1.2 Comparator**

Not applicable

### **4.2 Packaging and Labeling**

#### **4.2.1 Packaging**

Investigational medicinal products supplied will be SGI-110 for injection, 100 mg and SGI-110 diluent for reconstitution, 3 mL in 2 separate vials. Each vial is closed with a fluororesin laminated rubber stopper and a blue flip-off cap for SGI-110 for injection, 100 mg or a white flip-off cap for SGI-110 diluent for reconstitution, 3 mL.

